4.5.1 Early Termination Study Visit

Subjects who withdraw from the study before the 12 month follow-up visit will not be included in the final analysis of the study.

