The subjects will be identified/recruited during clinic hours as patients requiring an elective or traumatic foot and ankle surgery. During the clinic hours the primary investigator and/or the co-investigator will obtain full consent from the patient. We will recruit a minimum of 115 participants into each of two study arms, an immediate weight-bearing arm and a non-weight-bearing arm, so 230 participants will be included. Patients will be eligible if they are undergoing elective or traumatic foot and ankle surgery. Exclusion criteria will include any patient less than 18 years of age & over 89, history of foot or ankle surgery on the surgical limb, any degree of diagnosed peripheral neuropathy or peripheral vascular disease, infection, and/or unwillingness to participate at random in one of the two study arms.

Study Interventions and Measures:

We will be assessing the difference in two groups; immediate protected weight-bearing in a CAM walking boot vs strict non-weight-bearing for 6 weeks following foot and ankle surgery. Monitoring will be done by way of clinical follow-up, serial radiographs and/or other appropriate imaging modalities, and patient reported outcomes by way of AOFAS and SF-36 surveys.

Surgical procedures performed on patients included in the study will vary, as will the outcome measures for each procedure. Osseous fusions, including both elective joint fusions and bone healing following trauma, will be assessed by both clinical and radiographic evaluation. Soft tissue procedures, including elective stabilization and traumatic soft tissue repairs, will be assessed clinically and with imaging modalities

deemed appropriate. Complications during the perioperative and post-operative periods, such as non-union, infection, etc. will be included in the outcomes. All participants will also complete AOFAS and SF-36 surveys in the pre-operative and post-operative periods. We will also include return to work, activity, sport, etc. where appropriate.

Study Phase	Screening	Surgery	Post-op 2-3 w	Post-op 6-8 w	Post-op 3 m	Post-op 6 m	Post-op 1 yr	Post-op 2 yr	Unscheduled Visits
Visit Number	1		2	3	4	5	6	7	
Informed									
Informed Consent/Assent	x								
Review Inclusion/Exclusion									
Criteria	х								
Randomization	x								
Demographics/PMH	x								
Physical Examination	x		x	x	x	x	x	x	x
Adverse Event Assessment			x	x	x	x	x	x	x
Radiographs/Imagining	х		x	x	x	x	x	x	x
Complete AOFAS/SF- 36 survey	x			x	x		x	x	

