4.4 Unscheduled Visits

Unscheduled visits necessary to address any post-operative complications will be included in the patients study record. At no time will the welfare of the patient be compromised for the execution of the study. If at any time it is decided that a patient should be withdrawn from one of the two study arms, it will be recorded in the study results.

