4.5 Subject Completion/Withdrawal

Subjects may withdraw from the study at any time without prejudice to their care. They may also be discontinued from the study at the discretion of the Investigator for lack of adherence to study treatment or visit schedules, or AEs. The Investigator may also withdraw subjects who violate the study plan, or to protect the subject for reasons of safety or for administrative reasons. It will be documented whether or not each subject completes the clinical study

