6.2 Secondary Endpoints

The secondary outcome measures are the frequency of complications during the perioperative and post-operative periods, osseous healing as assessed by both clinical and radiographic evaluation, and healing outcomes of soft tissue procedures. These results will be analyzed at the end of the follow-up period.

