Descriptive statistics on the physical and mental component scores and the eight subdomain scores from the SF-36 will be reported for the immediate weight-bearing and non-weight bearing groups. In order to examine differences in SF-36 scores within each group over time, a one-way repeated measures ANOVA will be conducted to determine if the SF-36 scores are significantly different between visits (e.g., screening, post-operative at 6-8 weeks, post-operative at 12 months, and post- operative at 24 months). A two-way repeated measures ANOVA will be conducted to determine if the SF-36 scores are significantly be conducted to determine if the SF-36 scores are significantly be conducted to determine if the SF-36 scores are significantly be conducted to determine if the SF-36 scores are significantly be conducted to determine if the SF-36 scores are significantly be conducted to determine if the SF-36 scores are significantly be conducted to determine if the SF-36 scores are significantly be conducted to determine if the SF-36 scores are significantly different between the two groups for these same visits. Post-hoc pairwise comparisons using Tukey's test or Dunn's procedure will be performed, as indicated.

Descriptive statistics on the pain, function and alignment component scores from the AOFAS will be reported for the immediate weight-bearing and non-weight bearing groups. In order to examine differences in AOFAS scores within each group over time, a one-way repeated measures ANOVA will be conducted to determine if the AOFAS scores are significantly different between visits (e.g., screening, post-operative at 6 – 8 weeks, post-operative at 12 months, and post-operative at 24 months). A two-way repeated measures ANOVA will be conducted to determine if the AOFAS scores are significantly different between visits. Post-hoc pairwise comparisons using Tukey's test or Dunn's procedure will be performed, as indicated.

The chi-square test will be used to examine the frequency of complications during the perioperative and post-operative periods, osseous healing as assessed by both clinical and radiographic evaluation and frequency of soft tissue procedures between the immediate weight-bearing and non-weight bearing groups.

Logistic regression analysis will be performed to assess which patient characteristics and surgical characteristics are associated with higher SF-36 scores and AOFAS scores.

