7.3 Regulatory and Ethical Considerations

7.3.1 Data and Safety Monitoring Plan

The principal Investigator (P.I.) will be responsible for the ongoing data safety monitoring and oversight for the study sites. Study progress will be reviewed and submitted to the Institutional Review Board (IRB) annually.

The study would be discontinued if there is clear evidence that subjects in the early weight bearing study arm are encountering higher rates of complications compared to the control arm, non-weight bearing (NWB). This would be determined by an outside statistician ([name], LLC) that will review the data and adverse events after the first 10

patients have been enrolled in each study arm. Complications would include evidence of higher than expected non-unions, mal-union, uncontrolled pain, or wound complications, as evaluated for which specific surgical procedures were performed, any potential risk factors the patient carried, and patient compliance within the study protocol, and then treated appropriately for their risk of altered or inferior post-operative care.

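### Section 4.5.1 drops everyone who withdraws before the 12-month visit, so the final score and complication comparisons need not be of the groups as assigned

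*Combined protocol and SAP*

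**What the plan says.** Section 4.5.1 gives the rule: "Subjects who withdraw from the study before the 12 month follow-up visit will not be included in the final analysis of the study". It carries no condition on reason, arm or endpoint.

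Its parent, section 4.5, lists how subjects leave. They may withdraw by choice. They may be "discontinued from the study at the discretion of the Investigator for lack of adherence to study treatment or visit schedules, or AEs". And "The Investigator may also withdraw subjects who violate the study plan, or to protect the subject for reasons of safety or for administrative reasons".

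The primary endpoints (6.1) are the AOFAS and SF-36 scores. Table 1 schedules these surveys at screening, 6-8 weeks, 3 months, 1 year and 2 years. Complications are a secondary endpoint, for which section 6.2 says "These results will be analyzed at the end of the follow-up period"; section 6.4.1 adds that "The chi-square test will be used to examine the frequency of complications during the perioperative and post-operative periods".

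Two other statements touch the point. The Abstract (Study Interventions and Measures) says "Complications during the perioperative and post-operative periods, such as non-union, infection, etc. will be included in the outcomes", without naming an analysis population. Section 4.4 says that if it is decided that "a patient should be withdrawn from one of the two study arms, it will be recorded in the study results".

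**The concern.** This is a written post-assignment exclusion, not a missing detail. The grounds for leaving in section 4.5 can depend on arm and on outcome. Adherence means something different in each arm: protected walking in a boot, or strict non-weight-bearing for 6 weeks. Section 6.8 lists pain, wound problems, hardware failure and non-union as risks of the weight-bearing arm. The events the trial has to compare are therefore possible reasons for removing a subject from the comparison.

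Followed as written, the rule would discard surveys those subjects had already completed (screening, and 6-8 weeks and 3 months if reached). It would also take their complications out of the end-of-study chi-square test. Section 1.1 asks whether immediate weight-bearing is as safe and effective as the traditional course. A safety comparison restricted to those who stayed 12 months cannot be relied on to answer that.

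**Working it through.** **1. Does any other section restore these subjects?** Sections 6.3 to 6.5 contain no intention-to-treat statement, safety population, missing-data method or sensitivity analysis. Section 4.4 records withdrawals and section 6.8 records adverse events, but neither puts a subject back into a between-arm test. Section 7.3.1 has an outside statistician "that will review the data and adverse events after the first 10" patients in each arm are enrolled. That is a between-arm look, but an early one on a small part of the trial.

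**2. The plan's own figure (section 6.5).** At d = 0.40, two-sided 5% and 100 per arm, exact t-test power is 80.4%, so the stated 80% reproduces. Adding 15 gives 115 per arm; 15/115 = 13.0%. This allowance protects numbers. It does nothing about who is lost.

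**3. Scores (assumed inputs, no true effect).** Suppose a share f of an arm is excluded and those subjects score g SD worse than the rest. The full-arm mean is then the stayers' mean minus f × g, so exclusion raises the arm's mean by f × g. Between arms, bias = (k1 − k0)/115 × g, where k1 and k0 are the numbers selectively excluded. Any other losses are taken as random. Type I error is the rejection rate of the section 6.5 t-test with 100 per arm (noncentrality = bias × √50). The 15 per arm covers loss over the whole study, so here it is an upper input.

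| k1 v k0 | Bias (SD) at g = 0.5 / 1.0 / 1.5 | Type I error |
|---|---|---|
| 5 v 0 | 0.022 / 0.043 / 0.065 | 5.3% / 6.1% / 7.4% |
| 15 v 0 | 0.065 / 0.130 / 0.196 | 7.4% / 15.1% / 28.0% |
| 15 v 5 | 0.043 / 0.087 / 0.130 | 6.1% / 9.4% / 15.1% |
| 15 v 10 | 0.022 / 0.043 / 0.065 | 5.3% / 6.1% / 7.4% |

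**4. Complications (assumed inputs).** Let p be the true rate, wc the share of complicated subjects withdrawn, and wu = 0.10 the share of uncomplicated subjects withdrawn. Analysed rate = p(1 − wc) / [p(1 − wc) + (1 − p)(1 − wu)]. Share of the arm withdrawn = p × wc + (1 − p) × wu. The comparison arm has wc = 0.10, so its analysed rate equals p.

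| p | wc in one arm | Analysed rate | Other arm | Share of arm withdrawn |
|---|---|---|---|---|
| 10% | 20% | 0.08/0.89 = 9.0% | 10.0% | 11% |
| 10% | 30% | 0.07/0.88 = 8.0% | 10.0% | 12% |
| 10% | 50% | 0.05/0.86 = 5.8% | 10.0% | 14% |
| 5% | 50% | 0.025/0.88 = 2.8% | 5.0% | 12% |
| 20% | 50% | 0.10/0.82 = 12.2% | 20.0% | 18% |

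A real difference can also shrink. With true rates of 20% v 10%, and 30% of complicated subjects in the first arm but 10% of everyone else withdrawn, the analysed rates are 0.14/0.86 = 16.3% v 10.0%. The difference falls from 10.0 to 6.3 points.

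**5. No-bias case.** If withdrawal is unrelated to arm and outcome, the expected comparisons are unchanged.

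**The case against.** **Reach.** Section 4.5 speaks of subjects who withdraw, subjects who are discontinued (non-adherence, adverse events) and subjects whom the investigator withdraws (plan violation, safety, administrative). Section 4.5.1 uses the active form, so it could be read as covering voluntary withdrawal only. The plan does not settle this, nor whether leaving an arm (4.4) is the same as leaving the study. But section 4.5 itself uses *withdraw* for removal on safety grounds, and voluntary withdrawal can also follow pain or burden. Outcome-related loss survives the narrow reading.

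**Harms are still overseen.** Adverse events are recorded and reported to the IRB, SAEs are followed until resolved or stable (6.10.1), and the principal investigator monitors safety throughout. That is true, and subjects with complications who stay 12 months are still analysed. None of it supplies a between-arm comparison that includes those who left.

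**The figures are assumptions.** This stands. No document supports a particular differential withdrawal rate, and many settings lie close to 5%. The 50% settings at true rates of 10% and 20% imply 14% and 18% of that arm withdrawn, above the 13.0% allowance. The t-test is the basis of the power calculation, whereas the planned score analysis is a repeated-measures ANOVA.

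**Assignment.** Section 3.1 alternates every patient after the first coin flip, so the groups to be preserved are the groups as assigned. That is a separate matter and does not justify the exclusion.

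**Conclusion.** The concern holds and needs correction before the final analysis. As written, the rule makes membership of the analysed groups depend on staying to 12 months, and section 4.5 allows reasons for leaving that relate to arm and outcome.

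The size is unknown. Under the stated assumptions it runs from negligible (0.02 SD, type I error near 5%; 9.0% v 10.0% complications) to serious (0.20 SD, 28%; 5.8% v 10.0%). The upper score figure needs 15 exclusions in one arm averaging 1.5 SD worse and only random loss in the other. The case for changing the rule rests on the design principle, not on those upper figures.

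**What to change.** - Delete the section 4.5.1 exclusion and analyse all assigned subjects in their assigned arm.
- Use AOFAS and SF-36 surveys collected up to withdrawal in a method that accepts incomplete follow-up, such as a mixed model for repeated measures. This also deals with subjects who leave between 12 and 24 months, whom section 4.5.1 does not mention.
- Count complications for all operated subjects up to last contact. Report by arm how many were assigned but not operated on.
- Report follow-up time by arm and add one sensitivity analysis for unequal follow-up (time-to-event, or rate per follow-up time). Report healing outcomes with the number not assessable by arm.
- Report withdrawals by arm and reason.
- Show 12-month completers as a supporting analysis. Non-adherence can dilute differences and so favour a finding of similarity, which matters under the equivalence-or-better objective in the Abstract.
- Reconcile the Abstract and sections 4.4, 4.5 and 4.5.1 on whether leaving the assigned arm means leaving the study. The investigator's discretion to withdraw a subject for safety is not affected.

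**Cost.** Protocol and SAP wording, one change of repeated-measures method and one sensitivity analysis. No new visits are needed: surveys and adverse events are already collected up to withdrawal.

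**Limits that remain.** The mixed model assumes that missingness is explained by the observed data. A crude complication count is low in the arm that leaves sooner: if 15 of 115 leave before a 10% event could be seen, it gives 0.10 × 100/115 = 8.7% v 10.0%. Permitted use of withdrawn subjects' data must be checked against the consent form, which is not in the documents reviewed.

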5 STUDY EVALUATIONS AND MEASUREMENTS

5.1 Screening and Monitoring Evaluations and Measurements

5.1.1 Medical Record Review

The following will be abstracted from the medical chart:

- Patient age
- Past Medical history
 - Diabetic vs non-diabetic
 - Height/Weight (BMI)

- Smoker vs past-smoker vs non-smoker.
- Past surgical history
- Occupation and activities

5.1.2 Physical Examination

Physical examination will include evaluation of the dermatologic neurologic, vascular, and musculoskeletal systems of the lower extremities.

5.1.3 Radiographic/Advanced Imaging

X-rays, CT, MRI, and/or ultrasound will be obtained, when indicated, at certain visits determined by the physician. These imaging modalities will evaluate bone healing, joint fusion, and soft tissue repair integrity.

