4 STUDY PROCEDURES

4.1 Screening Visit

Below is a list of all of the procedures to be performed at each visit.

- Informed Consent
- Physical Exam
- Radiographic/Advanced Imaging
- Medical Record Review
 - Review of the medical record will include reviewing the past medical and surgical history, laboratory values, and most recent visits to other health care providers in the standard fashion of any office or inpatient encounter
- Surgical procedure discussed and operative consent
- Pre-operative AOFAS and SF-36 surveys completed

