4.3 Follow-up Phase

Follow-up Visit 1 (2-3 weeks post-op)

- Physical Exam
- Radiographic/Advanced Imagining
- Sutures removed
- Medical Record Review

Follow-up Visit 2 (6-8 weeks post-op)

- Physical Exam
- Radiographic/Advanced Imagining
- Post-op AOFAS and SF-36 survey
- Medical Record Review

Follow-up Visit 3 (3 months post-op)

- Physical Exam
- Radiographic/Advanced Imagining
- Post-op AOFAS and SF-36 survey
- Medical Record Review

Follow-up Visit 3 (6 months post-op)

- Physical Exam
- Radiographic/Advanced Imagining
- Medical Record Review

Follow-up Visit 4 (12 months post-op)

- Physical Exam
- Radiographic/Advanced Imagining
- Post-op AOFAS and SF-36 survey
- Medical Record Review

Follow-up Visit 5 (24 months post-op)

- Physical Exam
- Radiographic/Advanced Imagining
- Post-op AOFAS and SF-36 survey
- Medical Record Review

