6.4 Statistical Methods

6.4.1 Analysis of Primary Outcome of Interest

All analysis will begin with assessment of the normality of continuous variables using the Kolmogorov-Smirnov test. Normally distributed continuous variables will be reported as means and standard deviations; non-normally distributed data as median and interguartile range. Categorical data will be reported as counts and percentages. The Student's t-test will be used to compare continuous demographic and clinical data between the immediate weight-bearing and non-weight-bearing groups. The chi-square test or Fisher's exact test will be used to compare categorical data between groups. Cronbach's alpha will be used to measure reliability, or internal consistency, of both the Medical Outcomes Study 36-Item Short Form Health Survey (SF-36) and the AOFAS Ankle-Hindfoot Scale survey (AOFAS). Spearman's rank correlation coefficient will be used to assess the relationship between the physical and mental component scores and the eight subdomain scores from the SF-36 and the pain, function and alignment scores of the AOFAS. SF-36 scores and AOFAS scores will be adjusted for patient age, gender, BMI and presence of diabetes mellitus. Nonparametric tests will be used when data breaks the normality assumption. A value of p<.05 on twotailed testing will be considered statistically significant. Statistical analysis will be performed using IBM-SPSS Statistics, version 24.0 (IBM-SPSS Inc., Armonk, NY). Using one-way repeated measures analysis of variance (ANOVA), differences over time in radiographic and advanced imaging parameters will be assessed separately for the immediate weight-bearing and non-weight-bearing groups. Two-way repeated measures ANOVA will be used to assess differences over time in these parameters between the two groups. Tukey's test or Dunn's procedure will be used for post-hoc pairwise comparisons, as indicated.

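### Section 5.1.3 leaves the taking and timing of all imaging, plain films of bone included, to the physician, in conflict with the fixed schedule in Table 1, 4.1 and 4.3

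*Combined protocol and SAP*

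**What the plan says.** **Schedule.** The row "Radiographs/Imagining" in Table 1 is marked at screening, at 2-3 weeks, 6-8 weeks, 3 months, 6 months, 1 year and 2 years, and at unscheduled visits. Section 4.1 lists "Radiographic/Advanced Imaging" at screening. Section 4.3 lists "Radiographic/Advanced Imagining" under each of the six post-operative visits. None of these entries carries a condition.

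**Abstract (Study Interventions and Measures).** Bone and soft tissue are treated differently. For bone: "Osseous fusions, including both elective joint fusions and bone healing following trauma, will be assessed by both clinical and radiographic evaluation". For soft tissue, elective stabilizations and "traumatic soft tissue repairs, will be assessed clinically and with imaging modalities" judged appropriate.

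**Section 5.1.3.** One sentence covers all four modalities, plain X-rays among them, and says they "will be obtained, when indicated, at certain visits determined by the physician".

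**Use of the images.** Section 6.2 makes "osseous healing as assessed by both clinical and radiographic evaluation" a secondary outcome, and 6.4.1 compares it between arms by chi-square. For imaging parameters, 6.4.1 also plans: "Two-way repeated measures ANOVA will be used to assess differences over time in these parameters between the two groups".

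**The concern.** Matching the modality to the procedure is sensible. But 5.1.3 goes further and leaves open whether a plain film of a fusion or fracture is taken at all, and at which visit. A site reading the protocol cannot tell whether a 3-month film of an asymptomatic fusion is required.

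This matters because the person deciding can usually be expected to know the arm. No section describes blinding of the treating physician, and the arms are visibly different (walking in a boot against strict non-weight-bearing). Sections 6.8 and 7.3.2.6 name hardware failure and non-union as risks of the study arm, and 7.3.2.6 says that the control arm carries no added risk. A physician holding that view might find imaging indicated more readily in one arm. Even if the arms were imaged equally, skipped films would leave gaps in a series that is to be analysed over time, and a film not taken cannot be recovered at analysis.

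**Working it through.** The point is a conflict of text, so the main check is to set the places side by side.

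| Question | Table 1, 4.1, 4.3 | Abstract | 5.1.3 |
|---|---|---|---|
| Are plain films for bone required? | Imaging listed, no condition | Yes, radiographic evaluation | Only when indicated |
| At which visits? | 1 screening + 6 post-operative = 7 | Per Table 1 | Those the physician picks |
| Is soft tissue imaging discretionary? | No distinction made | Yes | Yes |

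**Can the texts be reconciled?** If the condition in 5.1.3 governed only the choice of modality, they could. But the sentence also hands over the choice of visits, and it does not exempt plain X-rays. The modality-only reading leaves that part unexplained.

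**Is blinding described anywhere?** No. Section 6.3, on control of bias, does not mention it. The only use of the word is in the title of a cited trial in the reference list.

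**What could follow for the chi-square test?** Let the true non-union proportions be p1 (study arm) and p0 (control arm), and let s1 and s0 be the probabilities that a non-union is detected.

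- Observed difference = p1·s1 − p0·s0.
- If p1 = p0 = p, this becomes p·(s1 − s0). It is zero when detection is equal. Otherwise it takes the sign of s1 − s0, with no true difference present.
- If s1 = s0 = s < 1, it becomes s·(p1 − p0), so a true absolute difference shrinks.

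The documents give none of p1, p0, s1 or s0. Neither sign nor size can be computed.

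**What could follow for the ANOVA?** A classical repeated measures ANOVA uses patients with a value at every analysed visit. Section 6.4.1 does not name the visits for the imaging parameters and gives no rule for missing images. The loss of patients therefore cannot be computed either.

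**Is the planned sample size touched?** No. Section 6.5 rests on the questionnaires: d = 0.40, two-sided 0.05, 80% power.

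- Normal approximation: 2 × (1.960 + 0.842)² / 0.40² = 98.1, so 99 per arm.
- Noncentral t: 99.08, so 100 per arm, with power 0.804 at 100.
- Adding 15 per arm gives 115, or 230 in total.

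The stated figures reproduce, and no imaging quantity enters them.

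**The case against.** The strongest reply is that the schedule is stated several times and 5.1.3 is one loosely drafted descriptive sentence that pools four modalities for bone and soft tissue. On that view sites will follow Table 1, and nothing is lost. Part of this stands: 5.1.3 is not declared to override the schedule, and every consequence above is conditional on its being followed. But nothing says that the schedule prevails, and 5.1.3 is the section devoted to imaging.

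A second reply is that harm is limited. Section 7.5 calls radiographs standard of care, 7.3.2.7 says that the listed risks exist under either course, 7.3.2.8 promises close follow-up in both groups, and 4.3 lists a physical examination at every follow-up visit. Section 6.2 also analyses secondary outcomes at the end of follow-up, so skipped interim films matter less for eventual union than for the ANOVA. These points reduce the likely effect. They do not settle which films must exist.

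Some stronger readings are tempting and not supported:

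- **That study-arm patients will be imaged more and will show more non-unions.** The documents do not say that imaging will differ by arm. This is a possibility only.
- **That the prominence of fusion and fracture-fixation procedures on the data form measures the problem.** The form lists procedure types. It says nothing about patients, missing films or bias.
- **That the whole imaging ANOVA should be confined to plain films of bone.** Section 6.4.1 plans advanced imaging as well, and 6.2 includes soft tissue healing. The conflict gives no reason to drop either.

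**Conclusion.** The inconsistency is real and should be corrected. It concerns secondary and imaging outcomes only. If 5.1.3 is followed as written, radiographic osseous healing and the radiographic ANOVA would depend on films selected by clinical judgement, with a possible ascertainment bias or incomplete series of unknown size and direction. A reader might infer that the trial's main comparison is compromised. It is not: the AOFAS and SF-36 endpoints do not use the images.

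The conclusion rests on two premises: that 5.1.3 means what it says about visits, and that the absence of any blinding provision reflects the plan. If sites in practice follow Table 1 for every osseous patient, the effect on the data is nil and only the wording needs repair.

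**What to change.** **Section 5.1.3.** State that plain radiographs for osseous procedures are obtained at every visit marked in Table 1 and 4.3, identically in both arms. Keep clinical indication for CT, MRI, ultrasound, soft tissue imaging and any extra films.

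**Section 6.4.1.**

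- Base the radiographic union comparison, and the plain-radiograph part of the ANOVA, on scheduled-visit films in osseous patients.
- Keep the planned advanced-imaging and soft tissue analyses, and note that the timing of those images is by indication.
- Count problems found on extra imaging as complications.
- Report missed scheduled films and extra imaging by arm.

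**Cost.** Wording in two sections, one small reporting table, and slightly less physician discretion over films that the schedule already lists. No additional CT, MRI or ultrasound is required, and 7.3.2.5 describes the X-ray dose as minimal.

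**Limit.** This equalises when plain films are taken. It does not change who reads them or whether the reader knows the arm.
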